## 9. STUDY VISITS AND PROCEDURES

The overall and detailed schedule for study procedures and visits is provided in Appendix 1.

## 9.1. Visit 1 – Screening/Baseline (Week 0, Day 1)

#### 9.1.1. Informed Consent

Before the potential patient has undergone any study-related screening procedures, the nature of the study and the potential risks associated with it will be explained to the patient, and the patient will be given an opportunity to ask questions to his or her satisfaction. After all questions are answered, but before proceeding further, the patient must read and sign a written informed consent form. This signed informed consent form will be retained in the Investigator's study file, and the date the patient signed the form will be entered into the CRF. The patient will be provided with a copy of his or her signed and dated informed consent form. The patient will be required to sign all updated informed consents.

Separate written, signed informed consent must be obtained if the patient is to participate in the optional pharmacogenomic assessment.

## 9.1.2. Screening Overview

The first study visit, Visit 1, will be where the study is explained to the prospective study patient, where written informed consent will be obtained and documented, and where protocol-specified study procedures and assessments will be completed.

For patients enrolling into this study from the 12-week open label extension study, P303, the P306 Baseline Visit (Visit 1) date is intended to be the same date as the final visit of the 12-week open label extension study, P303. However, if there are extenuating circumstances, Visit 1 of P306 may occur within fourteen days of their final visit in P303 without repeating baseline assessments. If more than fourteen days elapse between the final visit of P303 and start of the P306 study, medical monitor approval will be required and baseline assessments will need to be repeated.

For patients enrolling directly from the double-blind lead-in study, P301, all Visit 1 assessments will be performed. These patients are also expected to enter the P306 study at the same time as their final P301 visit; however, if there are extenuating circumstances, then Visit 1 of P306 may occur within fourteen days of their final P301 visit.

Once the patient has provided written informed consent to participate and has met all relevant inclusion criteria, this patient is eligible to begin the open-label treatment period, starting at bedtime on the day of enrollment. The patient should be dispensed three bottles of TNX-102 SL tablets, along with dosing and storage instructions. The end-of-study information collected at the final visit of the 12-week open label extension study P303, or the Visit 1 assessments completed as part of this protocol, will be considered the baseline values for Study P306.

## 9.1.3. Patient Numbering

All patients who participated in the double-blind lead-in HONOR study will retain their original concatenated 6-digit site-patient number, i.e., all patients entering P306.

## 9.1.4. Pharmacogenomic Assessment

Patients should be offered the opportunity to participate in the pharmacogenomic assessment as soon as Protocol Amendment 01 has been approved and implemented at the clinical site. The blood draw for this assessment is not tied to any specific visit; instead, it should be obtained after the patient has reviewed and signed the separate pharmacogenomic testing informed consent form, irrespective of the visit at which the consent is signed.

## 9.1.5. Visit 1 Baseline Assessments/Procedures (Week 0)

The following assessments/procedures will be completed at Visit 1.

## For all patients:

- Obtain written informed consent to participate
- Inclusion criteria
- Review and transcribe new concomitant medications as well as those which are to be continued from the double-blind lead-in HONOR study or the 12-week open-label extension study P303
- Review and transcribe new AEs as well as those which are ongoing from the doubleblind lead-in HONOR study or the 12-week open-label extension study P303

For patients enrolling from the double-blind lead-in study, P301/HONOR only (or patients rolling over to study P306 more than 14 days after the final visit of the 12-week open-label extension study P303):

- Obtain vital signs, including weight. The height collected at baseline from the lead-in study will be utilized for body mass index (BMI) calculations in this study.
- Perform a visual exam of the oral cavity
- Have the patient complete the PROMIS-Sleep Disturbance scale and the SDS.
   Review each scale for completeness once done.
- Have the patient complete the BDI-II
- Conduct the C-SSRS after reviewing the results of the BDI-II
- Draw blood for clinical laboratory testing
- Review patient's lifetime psychiatric treatment history, demographic information and medical history to ensure the information recorded during the double-blind lead-in study is accurate and complete, as it will also be included in the extension study's database.

Only those patients meeting all of the inclusion criteria will be eligible to continue.

## For all patients:

After all study requirements for Visit 1 of P306 have been fulfilled, the patient will:

- Be dispensed 3 bottles of TNX-102 SL tablets and be instructed to begin dosing with study medication at bedtime, starting the evening of Visit 1;
- Receive instruction regarding proper sublingual dosing technique and the time of expected dosing; and
- Schedule the telephone Visit 2 (for patients enrolled from the double-blind lead-in study, P301/HONOR, only) and receive an appointment to return to the clinic for Visit 3.

## 9.2. Visit 2 (Telephone Visit: Week 2)

For patients enrolled from the double-blind lead-in study, P301/HONOR only: Visit 2 will be done as a telephone call to the patient and should be conducted after 2 weeks of treatment, on Day  $14 \pm 3$  days.

The following steps should be completed:

- Assess changes in concomitant medications
- Assess study drug compliance based on patient verbal report
- Assess occurrence of AEs, including any oral AEs and whether an unscheduled visit is indicated for an examination of the oral cavity
- Review patient instructions regarding drug dosing and storage
- Administer the 'Since Last Visit' C-SSRS telephonically

## 9.3. Visits 3, 4, and 5 (Weeks 7, 16, and 28)

These visits are conducted after 7, 16, and 28 weeks ( $\pm$  7 days) of treatment respectively. The following assessments and procedures are to be conducted at each of these visits in the following general order:

- Collect returned study medication from patient and perform drug accountability
- Assess study drug compliance
- Assess for changes in concomitant medications
- Assess for occurrence of AEs

if any oral AEs have been reported (other than numbness, tingling or bitter taste), perform and document an examination of the oral cavity

- Have the patient complete the "baseline" PCL-S (Visit 5 only)
- Have the patient complete the PROMIS-Sleep Disturbance Scale and the SDS.
   Review each scale for completeness once done.
- Have the patient complete the BDI-II
- Conduct the C-SSRS after reviewing the results of the BDI-II
- Vital signs and weight

- Draw blood for clinical laboratory tests (Visit 5 only)
- Urine pregnancy test (for women of child-bearing potential)
- Inspect the oral cavity and document findings, if any (Visit 5 only)
- Conduct the CGI-I, using the P306 baseline visit as comparison
- Dispense 4 new bottles of TNX-102 SL tablets at Week 7 (Visit 3). At Weeks 16 (Visit 4) and 28 (Visit 5), dispense 5 new bottles.

Review patient instructions regarding drug dosing and storage, and schedule appointment for next clinic visit.

## 9.4. Visit 6 (Week 40)

Visit 6 is to be conducted after 40 weeks ( $\pm 7$  days) of treatment in the extension study. At this visit, the patient (Track A only) will return all remaining study drug and the following assessments and procedures are to be completed in the following general order:

- Collect returned study medication from patient and perform drug accountability
- Assess study drug compliance
- Assess for occurrence of AEs
- Assess for changes in concomitant medications
- Obtain vital signs including weight
- Track A patients only: Draw blood for clinical laboratory tests
- For women of child-bearing potential, conduct urine pregnancy test
- Track A patients only: Inspect the oral cavity and document findings, if any
- Have the patient complete the PCL-S
- Have the patient complete the PROMIS-Sleep Disturbance Scale and SDS
- Have the patient complete the BDI-II
- Conduct the C-SSRS after reviewing the results of the BDI-II
- Conduct CGI-I comparing to the P306 baseline
- Track B patients only: Dispense 5 new bottles of TNX-102 SL tablets

## 9.5. Visit 7 (Week 52)

Track B patients only: Visit 7 is to be conducted after 52 weeks ( $\pm 7$  days) of treatment in the extension study. At this visit, the patient will return all remaining study drug and the following assessments and procedures are to be completed in the following general order:

Collect returned study medication from patient and perform drug accountability

- Assess study drug compliance
- Assess for occurrence of AEs
- Assess for changes in concomitant medications
- Obtain vital signs including weight
- Draw blood for clinical laboratory tests
- For women of child-bearing potential, conduct urine pregnancy test
- Inspect the oral cavity and document findings, if any
- Have the patient complete the PCL-S
- Have the patient complete the PROMIS-Sleep Disturbance Scale and SDS
- Have the patient complete the BDI-II
- Conduct the C-SSRS after reviewing the results of the BDI-II
- Conduct CGI-I comparing to the P306 baseline

## 9.6. Early Termination (ET)

In accordance with the Declaration of Helsinki, patients have the right to withdraw from the study at any time for any reason, and they will be advised of this right. The investigator and Tonix also have the right to remove patients from the study. Specific reasons for removal of a patient from the study could include, but are not limited to:

- An AE
- An illness that, in the judgment of the investigator or Tonix, might invalidate the study results or place the patient at risk
- The request of the patient, investigator, or Tonix, whether for administrative or other reasons
- Pregnancy

Patients who wish to terminate their participation in the study should be instructed to come to the clinic for an Early Termination Visit. The purpose of the Early Termination visit is to obtain critical information about the patient's participation, and should be scheduled preferably before there has been a substantial lapse in study medication usage. However, even if there has been a medication lapse, the patient should be encouraged to return to the clinic for this visit, and should be instructed to return all remaining study medication.

The following assessments and procedures are completed at this visit in the following general order:

- Collect returned study medication from patient and perform drug accountability
- Assess study drug compliance
- Assess for occurrence of AEs

- Assess for changes in concomitant medications
- Obtain vital signs including weight
- Draw blood for clinical laboratory tests
- For women of child-bearing potential, conduct urine pregnancy test
- Inspect the oral cavity and document findings, if any
- Have the patient complete the PROMIS-Sleep Disturbance Scale and SDS
- Have the patient complete the BDI-II
- Conduct the C-SSRS after reviewing the results of the BDI-II
- Conduct CGI-I comparing to the P306 baseline

Once these assessments have been completed, the patient may be discharged from the study, provided there is no need for additional follow-up to continue to monitor an AE or other condition.

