## 6.3. Study Endpoints

## **6.3.1.** Safety

Safety will be assessed by:

- Adverse events (AEs) and serious AEs (SAEs) throughout the entire duration of the study, including assessment of AEs involving the oral cavity
- Change from baseline in clinical laboratory test results
- Changes from baseline indicative of increased suicidal ideation or behavior as assessed by the Columbia Suicide Severity Rating Scale (C-SSRS)
- Change from baseline in Beck Depression Inventory-II (BDI-II)
- Changes from baseline in vital signs and weight
- Track A patients only: Change from Visit 5 to Visit 6 in PTSD Checklist-Specific Version (PCL-S)
- Track B patients only: Change from Visit 5 to Visit 7 in PTSD Checklist-Specific Version (PCL-S)

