## 10.2.5. PTSD Checklist-Specific Version (PCL-S)

Developed by the National Center for Posttraumatic Stress Disorder, the PCL-S is a 17-item self-report measure reflecting DSM-IV symptoms of PTSD. The PCL-S aims to link symptom endorsements to a specified event or stressful experience, which for P306 has been identified by the subject as their Index Trauma during the lead-in double blind study (TNX-CY-P301). Respondents rate each item from 1 ("not at all") to 5 ("extremely") to indicate the degree to which they have been bothered by that particular symptom over the past month.

In addition, the long-term safety of TNX-102 SL on PTSD based on PCL-S completed by patients in Visit 5 (Week 28) and Visit 6 (Week 40) and Visit 7 (Week 52 for patients enrolled under Track B), is assessed with this scale. The mean change in PCL-S total score and PCL-S clusters scores from Visit 5 (Week 28) to Visit 6 (Week 40), or to Visit 7 for Track B patients will detect any potential worsening in total PTSD score or symptoms clusters in the final 12-weeks, or 24-weeks for Track B patients, of the study. Since PCL-S is added to the study when a significant number of patients have passed the Visit 4 (Week 16 time point, Visit 5 (Week 28) is chosen as the "baseline" for PCL-S in order to capture the vast majority of the patients who enrolled in the study from its beginning.

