h Visit 5(Week 28) will be the "baseline" for PCL-S because it will capture the vast majority of the patients who have enrolled from the start of P306. The mean change in PCL-S total score and PCL-S clusters scores from Visit 5 (Week 28) to Visit 6 (Week 40), and to Visit 7 for Track B patients, will detect any potential worsening in total PTSD score or symptoms clusters due to long-term treatment of TNX-102 SL in the final 12-weeks, and 24-weeks for Track B patients, of the study.

<sup>i Track A patients only.

<sup>j Track B patients only.

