7.1.1 Adjustments for Multiplicity and Other Alpha Control

7.1.1.1 Multiplicity

No adjustments will be made from multiplicity and all p-values will be nominal.

7.1.2 Data Handling for Participants Who Discontinue Study Drug or Withdraw from the Study

Participants who withdraw/drop out from the study will have their ET visit data collected and included in the analysis based on the closest visit window (Week 7, 16, 28, 40, or 52). Visit windows will be assigned by splitting the periods between visits at the midpoint between the visits. If more than one record falls within the window, the one closest to the target date will be used in the analysis, with preference given to the scheduled visits in the case of equidistant visits.

Protocol: TNX-CY-P306 Page 15 of 36

Final v1.0

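### The PCL-S is not collected at Early Termination, so patients who leave after Week 28 are missing from a change score meant to detect PTSD worsening; the direction and size of any bias are unknown

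*Protocol*

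**What the plan says.** Protocol 6.3.1 lists the PCL-S change as a safety endpoint: Visit 5 to Visit 6 for Track A and Visit 5 to Visit 7 for Track B. Protocol 12.2 also uses the Visit 5 to Visit 6 change in both tracks to judge durability of response. Section 10.2.5 gives the purpose: the mean change "will detect any potential worsening in total PTSD score or symptoms clusters in the final 12-weeks" (24 weeks for Track B). The Appendix 1 footnote fixes the reference point: "Visit 5(Week 28) will be the 'baseline' for PCL-S".

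Sections 9.4 (Visit 6) and 9.5 (Visit 7) each contain the line "Have the patient complete the PCL-S", directly before the PROMIS and SDS item. Section 9.6 (ET) has "Have the patient complete the PROMIS-Sleep Disturbance Scale and SDS" but no PCL-S line. Appendix 1 has no ET column and marks the PCL-S only at Visits 5, 6 and 7.

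SAP 7.1.2 says that patients who withdraw "will have their ET visit data collected and included in the analysis based on the closest visit window", and that "Visit windows will be assigned by splitting the periods between visits at the midpoint between the visits". SAP 2.2.1 lists PCL-S changes from Week 28 to 40 and, for Track B, from Week 28 to 52 and Week 40 to 52.

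**The concern.** An endpoint intended to pick up deterioration is observed only in patients who are still attending. Some routes out of the study are linked to psychiatric state. Protocol 10.4.1.2 calls for withdrawal at a C-SSRS ideation score of 4 or 5. Section 9.6 names an adverse event as a possible reason for removal, and under 10.4.1 marked worsening of PTSD symptoms is itself reportable as an adverse event. If such patients leave between Weeks 28 and 40, they have a baseline PCL-S and nothing to compare it with. The reported mean change then describes those who stayed, and could look more stable than the experience of everyone who reached Week 28.

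**Working it through.** **1. Comparing the visit lists.** The Visit 7 list in Protocol 9.5 has 13 items. The ET list in 9.6 has 12, the same except for the PCL-S:

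| Item | Visit 6 | Visit 7 | ET |
|---|---|---|---|
| PCL-S | yes | yes | **no** |
| PROMIS and SDS | yes | yes | yes |
| BDI-II | yes | yes | yes |
| C-SSRS | yes | yes | yes |
| CGI-I against P306 baseline | yes | yes | yes |

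No other section supplies it. Sections 10.4.1.3 (oral cavity) and 10.4.1.5 (laboratory) do name ET; 10.2.5 (PCL-S) does not.

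**2. Who is lost, and from what.**
- Either track, leaves after Visit 5 and before Visit 6: lost from every PCL-S change.
- Track B, leaves after Visit 6 and before Visit 7: kept in the Week 28-40 change; lost from Week 28-52 and Week 40-52.

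**3. Does the SAP repair it?** The 7.1.2 rule can place only what was collected. The PCL-S is not in the mixed-model endpoint list (9.1.1), and no missing-data rule covers it. By contrast, 9.1.2 counts a missing CGI-I as non-response.

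**4. Size.** The plan states no figure to reproduce. Let *p* be the share of patients with a Visit 5 PCL-S who have no later one, *C* the completers' mean change and *L* the leavers' mean change.

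- Mean over all with a Visit 5 score: (1 − p)·C + p·L
- Reported mean: C
- Understatement of worsening: p·(L − C)

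Assumed ranges (not in the documents): p = 5% to 20%, L − C = 5 to 10 points.

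| p | L − C = 5 | L − C = 10 |
|---|---|---|
| 5% | 0.25 | 0.5 |
| 10% | 0.5 | 1.0 |
| 20% | 1.0 | 2.0 |

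Seventeen items scored 1 to 5 span 17 × 4 = 68 points, so this is 0.25/68 = 0.4% to 2.0/68 = 2.9% of the range. If L is below C, the sign reverses.

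**5. Would adding the form be enough under SAP 7.1.2?** Appendix 1 puts Visit 5 at Day 196 and Visit 6 at Day 280. The midpoint is (196 + 280)/2 = Day 238, or Week 34. An ET score before then falls in the Week 28 window and competes with Visit 5. The record nearer to target is kept, usually Visit 5, so the ET score is discarded. The reverse can also happen: with Visit 5 at Day 189 (7 days off target) and ET at Day 200 (4 days off), the ET score becomes the Week 28 value and displaces the baseline. For Track B the next midpoint is (280 + 365)/2 = Day 322.5, about Week 46, with the same problem against Visit 6.

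As an illustration, take C = 0, L = 10 and ET times spread evenly over Weeks 28 to 40, so that half the leavers are recovered. The windowed mean is 0.5p × 10/(1 − 0.5p):
- p = 5%: 0.25/0.975 = 0.26, against 0.5 with every leaver counted
- p = 10%: 0.5/0.95 = 0.53, against 1.0
- p = 20%: 1.0/0.9 = 1.11, against 2.0

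**The case against.** Worsening is not invisible at ET. Adverse events, including marked PTSD worsening, are collected there, and those leading to discontinuation are tabulated and listed (SAP 10.1.1). Withdrawal reasons are tabulated (SAP 8.1). CGI-I, BDI-II and C-SSRS are all done at ET, and Protocol 12.2 rests durability first on CGI-I, with the PCL-S in addition. This stands, but with a limit: none of these gives a PCL-S total or cluster score, and the CGI-I at ET is rated against the P306 baseline, not Week 28.

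The endpoint also carries modest weight. The study has no concurrent control and no sample-size calculation, and Protocol 12.2 itself expects little on long-term efficacy. Because the PCL-S starts at Week 28, patients who left earlier are outside the endpoint whatever is done at ET. All of this stands and limits the importance of the point.

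Finally, an ET score is not a clean substitute for a Week 40 score. Section 9.6 wants the visit held even after a lapse in medication, and the PCL-S asks about the past month, so an early ET score may overlap the Visit 5 recall period. That is a reason to label such scores, not to leave them uncollected.

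**Conclusion.** The omission is real, and nothing elsewhere in the protocol or SAP makes it good. Patients with a Visit 5 PCL-S who leave before Week 40 contribute no change score; Track B patients who leave later are missing only from the changes that end at Week 52. The mean change may therefore understate worsening, by 0.25 to 2.0 points if 5-20% leave and are 5-10 points worse than completers. Both ranges are assumptions, and the true size is unknown.

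A reader might infer that the bias always runs in the reassuring direction. The documents do not support that. Section 9.6 also lists administrative requests, other illness and pregnancy as reasons for removal, and these need not follow PTSD severity; the reassuring direction is plausible, not established. A reader might also infer that every dropout is lost from every PCL-S analysis, or that the existing window rule would handle an ET score once collected. Steps 2 and 5 of the working show that neither is so.

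This is a worthwhile correction to a descriptive endpoint. It does not undermine the safety evaluation as a whole.

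**What to change.** **Protocol.** Add the Visit 6 line, "Have the patient complete the PCL-S", to Section 9.6, limited to patients who have completed Visit 5, and add an ET entry to Appendix 1.

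**SAP.** Exempt the PCL-S from the 7.1.2 midpoint rule. Keep Visit 5 as its fixed baseline. Count an ET PCL-S obtained after Visit 5 as post-baseline, assigned to the next visit without a valid value, similar to the handling of laboratory and vital-sign ET data in SAP 10.2 and 10.4. Report the change from Visit 5 to the last available PCL-S beside the by-visit changes. Report also how many patients with a Visit 5 PCL-S have no later one, with reasons. Note that ET scores may follow a medication lapse or overlap the Visit 5 recall month.

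**If data collection has ended.** The protocol estimated the last patient's completion for September 2019, and the SAP's reference list includes a 2023 item, so this may already be the case. Then give the count with reasons alone, and state that the PCL-S results describe patients who stayed to Week 40 or Week 52.

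**Cost.** One 17-item self-report form at a visit that already takes place, which is a few minutes of patient time, plus a protocol amendment with ethics approval and a case report form change. The reporting step needs only SAP text and one table.

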## 9.7. Unscheduled Visits

Patients may need to be seen at other times than the scheduled study visits for additional safety assessments or to follow-up, as medically necessary, on clinical laboratory, physical examination, or other findings. In addition, if a patient calls between scheduled visits to report a visible lesion in the oral cavity or other concerning oral cavity AE, the patient should be asked to return to the clinic as soon as possible for an unscheduled oral cavity examination. Unscheduled examinations are NOT required for reports of oral numbness, tingling, bitter taste, or for other mild or transient AEs that are not concerning to the patient. If an additional study visit occurs, the date and nature of the visit will be documented in the CRF and in the source documents. The patient should be advised to bring study medication with them to the unscheduled visit.

